6.4.3. Subgroup Analysis

The mean change from baseline in the number of migraine days and headache days of at least moderated severity during the 4-week periods will be summarized for the following subgroup population of the patients.

- patients who are receiving any concomitant migraine preventive medications at baseline
- patients who are not receiving any concomitant migraine preventive medications at baseline
- patients who used topiramate for migraine in the past
- patients who used onabotulinumtoxinA for migraine in the past

The means \pm SE of monthly change from baseline values of number of migraine days and headache days of at least moderate severity will be plotted by month for subgroup of patients who are receiving or not receiving any concomitant migraine preventive medications for each treatment group.

7. SAFETY ANALYSIS

7.1. General

The safety population will be used for all safety analyses. The CM and EM patients will be combined if they receive the same treatment. Summaries will be presented by treatment group (loading dose of TEV-48125 at 675 mg followed by monthly TEV-48125 at 225 mg, monthly TEV-48125 at 225 mg, and quarterly TEV-48125 at 675 mg) as actually received and overall. In addition, the patients with CM and patients with EM will be summarized separately for their safety endpoints. The descriptive statistics will be presented by treatment group and visits/months for new patients and placebo-treated rollover patients, TEV-48125-treated rollover patients, and overall under the same treatment, unless otherwise specified.

The safety and tolerability endpoints for this study are as follows:

- occurrence of adverse events throughout the study
- changes from baseline in clinical laboratory (serum chemistry, hematology, coagulation, and urinalysis) test results
- abnormal standard 12-lead ECG findings
- changes from baseline in vital signs (pulse, systolic and diastolic blood pressure, body temperature, and respiratory rate) measurements
- abnormal physical examination findings
- abnormal local injection site tolerability findings (ie, erythema, induration, and ecchymosis) and occurrence of injection site pain
- suicidal ideation and behavior as suggested by the eC-SSRS

Safety and tolerability measures and time points are provided in [Table 1](#) (patients rolling over from the pivotal efficacy studies), [Table 2](#) (patients not rolling over from the pivotal efficacy studies), and [Table 3](#) (patients rolling over from the pivotal efficacy studies for ADA assessment only).

Adverse events collected for the ADA only analysis population will be listed separately.

7.2. Study Drug Administration

Patients rolling over from the pivotal efficacy studies who were randomized to the active treatment groups will continue receiving the same treatment (ie, monthly TEV-48125 at 225 mg or quarterly TEV-48125 at 675 mg) throughout this long-term safety and efficacy study. Patients rolling over from the pivotal efficacy studies who received placebo and the new patients will be randomly assigned in a 1:1 ratio using IRT as follows:

- Patients with CM will receive sc TEV-48125 at 675 mg (loading dose) followed by 11 monthly sc doses of TEV-48125 at 225 mg or sc TEV-48125 at 675 mg once every 3 months for 12 months for a total of 4 doses.
- Patients with EM will receive monthly sc TEV-48125 at 225 mg for 12 months or sc TEV-48125 at 675 mg once every 3 months for 12 months for a total of 4 doses

Study drug will be administered as sc injections approximately every 4 weeks (28 days).

In order to maintain the study blind, all patients will receive 3 injections at visits 2, 5, 8, and 11 and 1 injection at all other visits as detailed in [Table 5](#).

Table 5: Study Drug Administration by Treatment Group and Visit

Treatment group in this study	Visit 2	Visits 5, 8, and 11	Visits 3, 4, 6, 7, 9, 10, 12, and 13
Loading dose of TEV-48125 at 675 mg followed by monthly TEV-48125 at 225 mg	3 active injections (225 mg/1.5 mL)	1 active injection (225 mg/1.5 mL) and two 1.5-mL placebo injections	1 active injection (225 mg/1.5 mL)
Monthly TEV-48125 at 225 mg	1 active injection (225 mg/1.5 mL) and two 1.5-mL placebo injections	1 active injection (225 mg/1.5 mL) and two 1.5-mL placebo injections	1 active injection (225 mg/1.5 mL)
Quarterly TEV-48125 at 675 mg	3 active injections (225 mg/1.5 mL)	3 active injections (225 mg/1.5 mL)	one 1.5-mL placebo injection

Duration of treatment (days treated) is the number of days on treatment based on the first and EOT visit day/early withdrawal day (EOT visit day – first day of study drug + 1). For subjects who are lost to follow-up, the last day is defined as the last study drug administration date +27.

Number (%) of patients receiving ≥ 1 dose, ≥ 2 doses, ≥ 3 doses, and so on will be summarized using descriptive statistics by treatment group. Duration of treatment (days) and number of doses will also be summarized using descriptive statistics for each treatment group.

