First treatment administration (ie, for this study) will occur at visit 2, and additional doses will be administered at each visit (approximately every 4 weeks) through visit 13. Patients will return for the EOT visit (visit 14) approximately 4 weeks after administration of the final dose of study drug, and they will return approximately 7.5 months (225 days [the approximate equivalent of 5 half-lives]) after administration of the final dose of the study drug for collection of adverse event and concomitant medication information and samples for pharmacokinetic, immunogenicity, and biomarker analyses.

Headache information will be captured using an electronic headache diary device as follows:

- For patients rolling over from the pivotal efficacy studies, headache information will be captured daily during the first 3 months, during the 4-week period after visit 7, and during the 4-week period after visit 13.

- For patients not rolling over from the pivotal efficacy studies, headache information will be captured daily during the first 4 months, during the 4-week period after visit 7, and during the 4-week period after visit 13.

Assessments of migraine-related disability and change in quality of life (using the HIT-6 or MIDAS questionnaire, PHQ-2/PHQ-9, PGIC scale, MSQOL questionnaire, EQ-5D-5L questionnaire, and WPAI questionnaire), safety evaluations, and collection of pharmacokinetic, immunogenicity, and biomarker samples will be performed throughout the study according to the schedules of assessments ([Table 1](#), [Table 2](#), and [Table 3](#)) and [Section 3.14](#).

[figure not shown]
Patients who withdraw from the study before completing the 12-month treatment period will have EOT visit (visit 14) procedures and assessments performed at their final visit, and they will be asked to return for the follow-up visit approximately 7.5 months (225 days [the approximate equivalent of 5 half-lives]) after their last dose of study drug.

The study schemas for patients with CM and EM who receive study drug in the current study are presented in [Figure 1](#) and [Figure 2](#), respectively.

The end of the study is defined as the date the last patient attends the follow-up visit (visit 15).

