3.14.4. Procedures After Study Drug Treatment

3.14.4.1. Patients Rolling Over from the Pivotal Efficacy Studies and New Patients (Final Visit [Visit 15 (Day 533)])

Procedures after study drug treatment will be the same for patients rolling over from the pivotal efficacy studies who receive study drug during the current study and patients not rolling over from the pivotal efficacy studies.

Patients who participate in the study in compliance with the protocol for the entire treatment period (ie, from visit 2 through visit 14) will be considered to have completed the study. Patients may be treated with standard of care following completion of visit 14.

Patients who complete the treatment period will have a follow-up visit approximately 7.5 months (225 days [the approximate equivalent of 5 half-lives]) after administration of the final dose of study drug. The following procedures/assessments will be performed at this visit:

- Inquire about adverse events.
- Inquire about/review concomitant medications.
- Perform physical examination (including weight).
- Complete the eC-SSRS Since Last Visit version.
- Obtain a 4-mL blood sample for plasma TEV-48125 concentration determination.
- Obtain a 5-mL blood sample for serum ADA assessment.
- Obtain a 5-mL urine sample for biomarker analysis.
- Obtain an 18.5-mL blood sample (6 mL each for serum and plasma and 6.5 mL for RNA) for serum, plasma, and RNA biomarker analysis.

In addition, a single 6-mL blood sample for pharmacogenomics (DNA) may be obtained from patients who consent to pharmacogenomics analysis if the sample is not obtained at an earlier visit.

Patients who discontinue treatment prematurely must be encouraged to continue to attend the regular scheduled visits, and complete the prescribed safety and efficacy evaluations through the EOT visit and the follow-up visit, if at all possible.

Patients who both discontinue treatment and also withdraw from the study should have EOT (early withdrawal) visit procedures/assessments (see [Table 1](#) and [Table 2](#)) performed on the last day the patient receives the study drug, or as soon as possible thereafter. The patient should also return for the follow-up visit approximately 7.5 months after the last dose of study drug if at all possible.

Procedures for patients who withdraw prematurely from the study are described in [Section 4.4](#). As appropriate, patients should be treated with standard of care following termination of the study.

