4.4. Withdrawal Criteria and Procedures

In accordance with the Declaration of Helsinki (in accordance with the applicable country's acceptance), each patient is free to withdraw from the study at any time. The investigator also has the right to withdraw a patient from the study in the event of intercurrent illness, adverse events, pregnancy (see Section 7.2), or other reasons concerning the health or well-being of the patient, or in the event of lack of cooperation. In addition, a patient may be withdrawn from the study as described in Sections 3.12, 3.14.4, 5.4, and 7.1.7.

Should a patient decide to withdraw after administration of study drug, or should the investigator decide to withdraw the patient, all efforts will be made to complete and report all observations up to the time of withdrawal. A complete final evaluation at the time of the patient's withdrawal should be made and an explanation given as to why the patient is withdrawing or being withdrawn from the study.

The reason for and date of withdrawal from study drug treatment and the reason for and date of withdrawal from the study must be recorded on the source documentation and transcribed onto the CRF. If a patient withdraws consent, every attempt will be made to determine the reason. If the reason for withdrawal is an adverse event or a potentially clinically significant abnormal laboratory test result, monitoring will be continued at the discretion of the investigator (eg, until the event has resolved or stabilized, until the patient is referred to the care of a healthcare professional, or until a determination of a cause unrelated to the study drug or study procedure is made). The specific event or test result must be recorded on the source documentation and transcribed onto the CRF.

All protocol-specified procedures/assessments should be performed at the early withdrawal visit (see EOT/early withdrawal visit in Table 1 and Table 2). Patients who withdraw from the study will be asked to return to the clinical site for a follow-up visit approximately 7.5 months after their last dose of study drug. Immunogenicity, pharmacokinetic, and safety procedures/assessments will be performed at this visit (see Table 1 and Table 2).

A patient should only be designated as lost to follow up if the site is unable to establish contact with the patient after 3 documented attempts via 2 different methods (phone, text, e-mail, certified letter, etc.).

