^a Patients not rolling over from the pivotal efficacy study who meet eligibility criteria after completing a 28-day run-in period and patients rolling over from the pivotal efficacy study who received placebo will be randomized in a 1:1 ratio at visit 2 to receive a loading dose of TEV-48125 at 675 mg followed by monthly TEV-48125 at 225 mg or TEV-48125 at 675 mg quarterly.

^b For patients who begin this study (visit 2) on the same day as the EOT visit (visit 5) of the pivotal efficacy studies, the EOT visit procedures/assessments for the pivotal efficacy study must be completed before beginning visit 2 procedures/assessments.

EOT=end-of-treatment; NR=nonrollover patients; PBO=placebo; V=visit.

Figure 2: Study Schema for Patients with Episodic Migraine

^a Patients rolling over from the pivotal efficacy study who received placebo and patients not rolling over from the pivotal efficacy study who meet eligibility criteria after completing a 28-day run-in period will be randomized in a 1:1 ratio at visit 2 to receive quarterly TEV-48125 at 675 mg or monthly TEV-48125 at 225 mg.

^b For patients who begin this study (visit 2) on the same day as the EOT visit (visit 5) of the pivotal efficacy study, the EOT visit procedures/assessments for the pivotal efficacy study must be completed before beginning visit 2 procedures/assessments. EOT=end-of-treatment; NR=nonrollover patients; PBO=placebo; V=visit.

Table 1: Study Procedures and Assessments for Patients Rolling Over from the Pivotal Efficacy Studies

Study period	Pre-treatment period ^a	Treatment period													Follow-up period	
Visit number	V1	V2 ^b	V3	V4	V5	V6	V7	V8	V9	V10	V11	V12	V13	V14	V15	
Procedures and assessments (completed before dosing, when applicable, unless otherwise noted)	Screening days -28 to -1	Dose 1 day 0 (±5 days)	Dose 2 day 28 (±5 days)	Dose 3 day 56 (±5 days)	Dose 4 day 84 (±5 days)	Dose 5 day 112 (±5 days)	Dose 6 day 140 (±5 days)	Dose 7 day 168 (±5 days)	Dose 8 day 196 (±5 days)	Dose 9 day 224 (±5 days)	Dose 10 day 252 (±5 days)	Dose 11 day 280 (±5 days)	Dose 12 day 308 (±5 days)	EOT/early withdrawal day 336 (±5 days)	Final visit day 533 (±15 days)	
Informed consent		X														
Inclusion and exclusion criteria		X														
Randomization ^c		X														
Full physical examination, including weight		X ^d					X	X					X	X	X	
12-lead ECG ^e		X ^d												X		
Vital signs measurement ^e		X ^d	X	X	X	X	X	X	X	X	X	X	X	X		

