4.6. Study Days and Visit Windows

Study days will be numbered relative to the 1st day of study drug administration. The start of treatment (visit 2 or day 1) is defined as the date on which a patient receives the 1st dose of study drug, as recorded on the study drug diary. The 1st day for the patients rolling over from the pivotal efficacy studies will be the day when they receive the 1st dose of study drug after finishing their procedures/assessments for the pivotal study EOT visit ([Figure 1](#) and [Figure 2](#)). Days will be numbered relative to study start (ie, ..., -2, -1, 1, 2, ...; with day 1 being the start of study drug and day -1 being the day before the start of study drug).

The 4-week (28-day) visit windows for the e-diary based efficacy endpoints will be determined based on the actual dosing day. The run-in phase for the new patients is defined as day -28 to -1 before the 1st injection on day 1. Treatment is from the visit 2 to visit 14 or the EOT visit. Month 1 is from the date/time of the 1st dose of study drug administration on day 1 to the date/time just

before the 2nd dose. Month 2 is from the date/time of the 2nd dose to the date/time just before the 3rd dose. Month 3 is from the date/time of the 3rd dose, and so on.

Throughout this document, all by month efficacy summaries for the headache data will refer to these visit windows.

For all other by-visit summaries, if there are multiple assessments at a postbaseline visit then the last non-missing assessment at that visit will be used for the summary. This includes assessments at the scheduled and unscheduled visits.

Endpoint for analyses and summaries is the last observed postbaseline data. For patients who withdraw from the study, their safety data at the early termination visit will be excluded from the by-visit summaries but will be included in the endpoint summaries.

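### SAP 7.2 counts time after dosing has stopped as days treated: a one-dose patient who stays to the EOT visit gets a nominal 337 days, the same as a 12-dose completer, against 28 days if lost to follow-up

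*SAP*

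**What the plan says.** SAP 7.2 defines exposure time as follows: "Duration of treatment (days treated) is the number of days on treatment based on the first and EOT visit day/early withdrawal day". The formula attached to it is EOT visit day minus first day of study drug plus 1. One group is treated differently: "For subjects who are lost to follow-up, the last day is defined as the last study drug administration date +27". Numbers of doses are summarized in the same section.

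The documents treat the EOT/early withdrawal day as a visit:

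- The schedules in SAP Tables 1 and 2 give it a visit column, headed in Table 1 "EOT/early withdrawal day 336 (±5 days").
- Protocol 3.1 says that patients who withdraw from the study before completing treatment "will have EOT visit (visit 14) procedures and assessments performed at their final visit".
- SAP 4.6 says: "Treatment is from the visit 2 to visit 14 or the EOT visit".

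Protocol 3.14.4.1 separates two kinds of early stopper. For those who stop drug only, it says: "Patients who discontinue treatment prematurely must be encouraged to continue to attend the regular scheduled visits", and this runs through the EOT and follow-up visits where possible. For those who stop drug and also leave the study, the early withdrawal procedures are to be "performed on the last day the patient receives the study drug, or as soon as possible thereafter".

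Protocol 4.4 requires the two kinds of stopping to be dated separately: the reason for and "date of withdrawal from study drug treatment and the reason for and date of withdrawal from the study must be recorded". The SAP 7.2 formula does not use the drug withdrawal date.

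**The concern.** A single variable has two different end points, and how the patient left the study decides which applies. Patients lost to follow-up are counted to the end of their last dosing interval. Everyone else is counted to a visit, which for a patient who stops drug and stays can fall many months after the last injection. For a patient who stops and withdraws, the count depends on how soon the early withdrawal visit takes place. Patients with identical dosing histories can therefore get very different durations.

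The primary objective is long-term safety, and protocol 1.5 presents the study as giving patients in general at least 12 months of exposure. Duration of treatment is the SAP's only time-based summary of that exposure. A rule that gives early stoppers who remain under observation the same duration as completers overstates it.

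**Working it through.** **Inputs**

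- Dosing every 28 days, 12 doses: dose k falls on protocol day 28(k − 1), so dose 1 is on day 0, dose 6 on day 140, dose 11 on day 280 and dose 12 on day 308 (protocol Tables 1 and 2).
- EOT visit: day 336 ± 5 (protocol 3.14.3.1.11).
- Duration formula and lost-to-follow-up rule: SAP 7.2.

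**Check of the schedule.** 12 × 28 = 336, which matches the stated EOT day. Day 308 + 225 = 533, which matches the final visit. The documents give no duration figure to reproduce.

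**Duration under SAP 7.2, by route**

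- Stops drug and stays to EOT: 336 − 0 + 1 = 337 for any k. With the ± 5-day window, 332 to 342. SAP 4.6 numbers the first dosing day as day 1, which makes EOT day 337 and gives the same result: 337 − 1 + 1 = 337.
- Lost to follow-up: 28(k − 1) + 27 − 0 + 1 = 28k.
- Stops and withdraws: from 28(k − 1) + 1 if the visit is on the dosing day, to 28k + 1 if it is at the next scheduled visit.

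| Doses received | Stays to EOT | Lost to follow-up | Stops and withdraws |
|---|---|---|---|
| 1 | 337 | 28 | 1 to 29 |
| 6 | 337 | 168 | 141 to 169 |
| 11 | 337 | 308 | 281 to 309 |
| 12 (completer) | 337 | 336 | not applicable |

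**Excess for a patient who stops and stays**, over last administration + 27, is 337 − 28k:

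- k = 1: 337 − 28 = 309 days (304 to 314 with the visit window)
- k = 6: 337 − 168 = 169 days (164 to 174)
- k = 11: 337 − 308 = 29 days (24 to 34)

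**Effect on the mean.** The share of patients who stop drug but stay is not given; the anticipated 30% drop-out rate is not that figure. Per 1% of treated patients, the mean rises by one hundredth of the excess:

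- k = 1: 3.09 days, and 3.09 / 336 = 0.92%
- k = 6: 1.69 days, and 1.69 / 336 = 0.50%
- k = 11: 0.29 days, and 0.29 / 336 = 0.09%

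**The case against.** **The wording could mean the end of dosing.** SAP 7.2 speaks of days on treatment, and early withdrawal day could be taken as the drug withdrawal date that protocol 4.4 requires. The protocol also describes the EOT visit as about 4 weeks after the final dose, which would make the +27 rule nearly the same convention. But that description is of patients dosed through visit 13. The formula itself uses the EOT visit day, and the schedule tables, protocol 3.1 and SAP 4.6 all place the EOT/early withdrawal day at a visit. The reading does not survive the text.

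**Few patients may be affected.** Several routes off drug lead to withdrawal and so to an end date near the last dose: liver stopping rules with an early withdrawal visit (protocol Appendix E), a broken blind (3.8.2), and pregnancy as described in 7.3.5.1. This stands. It is why no overall error is claimed.

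**The drug persists.** With a half-life of about 45 days and a 225-day washout (protocol 3.11), a patient last dosed at dose 5 (day 112) reaches washout only at day 112 + 225 = 337. So only patients who stop after doses 1 to 4 have passed it by a nominal day-336 EOT visit. That is a fair caution against calling all the later time drug-free. It does not make it time on treatment, and the lost-to-follow-up rule credits no such persistence.

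**Dose counts sit beside the duration summary, and no exposure-adjusted rates are planned.** This also stands, and it limits the harm to one summary.

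**The ranges are not strict bounds.** Under protocol 5.1, a visit more than 5 days late resets the 4-week interval, and no deadline is set for the early withdrawal visit. They are nominal ranges only.

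**Conclusion.** The concern holds, as a minor point. Applied as written, SAP 7.2 gives a nominal 337 days to a patient dosed once who attends the EOT visit and to a 12-dose completer alike, and 28 days to a patient dosed once and lost to follow-up. These figures assume dosing and visits on their nominal days.

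The effect on a group mean depends on how many patients stop drug but stay, which the documents do not state. Only the rate of 0.3 to 3.1 days per 1% of treated patients can be given, for stops after dose 11 and dose 1 respectively. The conclusion is confined to the descriptive duration summary; dose counts and adverse event incidences are unaffected.

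**What to change.** In SAP 7.2, define the last day of treatment for every patient as the earliest of:

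1. last study drug administration + 27;
2. date of death;
3. for the interim report, the data cut-off date.

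Duration is then last day − first dose day + 1. State that placebo injections in the quarterly arm count as study drug administrations for this purpose, in line with SAP Table 5, which already lists them. The cut-off clause also supplies an end date for patients still on treatment at the interim cut-off (SAP 2.5.1). Such a patient has no EOT visit and is not lost to follow-up, so the present rule gives none. SAP 4.6 can stay as it is for the visit windows.

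The cost is two or three sentences and no new data. Completers change from a nominal 337 to 308 + 27 + 1 = 336 days, and mean duration may look slightly shorter. A quarterly-arm patient who stops after visit 2 is credited with 28 days although that regimen is given every 3 months. The present lost-to-follow-up rule already does this, but the new rule would apply it to every such early stopper, so the SAP should say so openly.
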